9.1. EVALUATION DURING TREATMENT & FOLLOWING TREATMENT

- 9.1.1. PRE-ENTRY ASSESSMENT: see section 4.7.
- 9.1.2. Stereotactic radiosurgery is an outpatient procedure. Patient management immediately after the procedure will follow routine patient care guidelines as determined by the physician. Subjects will be provided instructions on who to call with specific contact information, in the event they experience any untoward effects following treatment. In the event a subject experiences any untoward effects following CyberKnife treatment, information specific to the patient's condition and symptoms, treatment intervention required, and hospital stay and course will be recorded for purposes of clinical evaluation.
- 9.1.3. ACUTE ASSESSMENT: Patients will have toxicity evaluation and AUA score on the last day of treatment.
- 9.1.4. ASSESSMENTS FOLLOWING TREATMENT: at one week after treatment (allowed window: +/- 3 days), toxicity and AUA score will be evaluated. At 1 month (+/- 7 days) following treatment, patients will be assessed for acute toxicity, and will fill out AUA form, SF-12, EPIC-26, SHIM and Utilization of Sexual Rx/Devices. At 3, 6, 12, 18, and 24 month (+/- 2 wks) intervals (and every 6 months thereafter, through year 5), patients will be seen and evaluated, including a history, physical exam, ECOG performance status, PSA, toxicity evaluation, and AUA score. In addition, at 6 months, 12 months and annually thereafter, the SF-12, EPIC-26, SHIM and Utilization of Sexual Medications/Devices will be administered. After the 5 year follow-up patients will be seen yearly through year 10 (allowed window: +/-1 month) and the following will be performed: PSA, toxicity evaluation, and the following questionnaires will be administered: EPIC -26; AUA; SHIM. Examination and studies may

- be done at outside facility. A serum total testosterone will be measured at baseline and with every PSA through year 2.
- 9.1.5. PROSTATE BIOPSY will be performed at time of biochemical or local clinical failure, and is encouraged at 2 years following treatment and at time of distant failure.
- 9.1.6. BONE SCAN will be performed at the time of biochemical failure, or when the patient develops signs of symptoms suggesting metastatic disease.
- 9.1.7. Axial Imaging (CT or MRI) of the abdomen and pelvis will be performed at the time of biochemical failure, or when the patient develops signs of symptoms suggesting metastatic disease.

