We chose N large enough to test the null hypothesis against the alternative hypothesis with power equal to 80% at the one-sided 5% significance level.

Let Z_u denote the upper u-th percentile of the standard normal distribution. Hence $Z_{.05} = 1.645$ corresponding to the one-sided 5% level of significance and $Z_{.20} = 0.84$ corresponds to 80% power. Then the sample size is determined by Formula 1:

$$N = \frac{\left[z_{\beta}\sqrt{\pi_{1}(1-\pi_{1})} + z_{\alpha}\sqrt{\pi_{0}(1-\pi_{0})}\right]^{2}}{\left[\pi_{1} - \pi_{0}\right]^{2}}, \text{ where}$$

 π_1 is the expected proportion of CyberKnife treated patients bDFS at 5 years if the alternative hypothesis is true; the bDFS rate is then expected to equal or exceed 0.94. For purposes of sample size estimation, we require 80% power if $\pi_1 \geq 0.945$. π_0 is the expected lower limit of the 95% confidence interval for π and is set equal to 0.90. Then N= 232. Allowing 8% sample size degradation for lost to follow-up, the sample size must be increased to 232/.92 = 253 subjects.

Primary Safety Objective

The primary safety objective is to establish with 95% confidence that the percentage of CyberKnife treated patients experiencing \geq Grade 3 toxicity is not more than 5% higher than the approximately 9% 5-year rate extrapolated from Table 2, Section 1.15.

With N=232 CyberKnife treated subjects, if the observed \geq Grade 3 toxicity rate equals 9%, then with 95% confidence the "true" rate \leq 12.6%. Since the difference between 12.6% and 9% is less than 5%, the sample size of 232 subjects is more than large enough to meet the primary safety objective.

11.3.1 ACCRUAL RATE: the initial three months while institutions are obtaining IRB approval, therefore we do not expect to meet the targeted monthly accrual rate until after the first three months. The estimated accrual rate is 2 patients per study site per month. Expectations of 5 treating study sites assumes an accrual period of approximately 29 months total.

11.4STATISTICAL METHODS

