11.4.2. SECONDARY OBJECTIVES

1. Local and Distant Tumor Control

As defined in Section 9.4, the failure to achieve local and distant tumor control will be documented for each patient. These rates will be summarized and descriptive statistics (standard deviations, confidence intervals) will calculated.

2. Quality of Life Assessments

The SF-12 total score, AUA score, EPIC-26 total score and the EPIC-sexual domain sub score are used to quantify quality of life (QoL) at baseline and repeatedly during the post treatment period (see Section 9.0). We will use the generalized estimating equation (GEE) method to provide valid inferences. This method was originated to make inference about average behavior, where the dependent variable depends not only on the "explanatory" variable (time measured in months) but also on the correlation of a patient's repeated measurements. The GEE approach fits the model to the observed data as closely as possible, weighting each patients' "cluster" of measurements over time inversely to its variance - covariance matrix. With this method, no imputations are required and all data recorded is use in the analysis. Other important features of GEE are that no distributional assumptions for the dependent variable are required to use the method and in most cases valid inferences are provided even when the correlation structure is miss-specified. For each score, we will use GEE to fit a straight line to patients' longitudinal course of repeated values. We hypothesize that immediately following treatment, the GU & GI subsections of the EPIC-26 and the AUA will demonstrate a worsening of GU and GI function, but this will return to normal with time. We further hypothesize that the sexual function subset of the EPIC-26 will show gradual worsening function relative to baseline over the five-year follow-up period. These QOL outcomes will be compared to those reported in other prospective studies using the same instruments, including RTOG 0232

and 0415. We hypothesize that the slope of a fitted line will not be significantly less than zero; that is, QoL will be maintained throughout the assessment period.

3. Adverse Events

All adverse events will be recorded on the case report forms. For both acute (<=90 days of treatment start) and late (>90 days of treatment start), the frequency and proportion of each type of adverse event will be presented in tabular form, on both a per-patient and a per-event basis.

4. Survival

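### If return of quality-of-life forms depends on earlier scores, the GEE slope depends on a working correlation the plan does not name, and the plan's validity statement omits this condition

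*Combined protocol and SAP*

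**What the plan says.** Section 11.4.2 (Quality of Life Assessments) analyses the SF-12 total, AUA, EPIC-26 total and EPIC sexual scores by GEE. Each patient's cluster "of measurements over time inversely to its variance - covariance matrix" is weighted, and for each score "we will use GEE to fit a straight line". On missing data it says only that "With this method, no imputations are required and all data recorded is use in the analysis". On the covariance it says that "in most cases valid inferences are provided even when the correlation structure is miss-specified"; no working correlation is named.

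The reading rule is: "We hypothesize that the slope of a fitted line will not be significantly less than zero", which the section equates with QoL being maintained. The same section expects that the EPIC sexual subset "will show gradual worsening function relative to baseline over the five-year follow-up period".

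Forms are collected at baseline and 1 month, and then (section 9.1.4) "at 6 months, 12 months and annually thereafter, the SF-12, EPIC-26, SHIM and Utilization of Sexual Medications/Devices will be administered". The only loss rate in the documents is in the bDFS sample size, section 11.3: "Allowing 8% sample size degradation for lost to follow-up". Section 14.6 says withdrawn men may be asked to continue PSA tests and examinations; it does not mention questionnaires. The documents give no missing-data assumption for QoL, no response weighting, no sensitivity analysis and no target for form return.

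**The concern.** GEE tolerates a wrong working correlation when data are complete or missing completely at random. If the chance of returning a form depends on earlier scores, that tolerance is lost. The men still observed late in follow-up are then a favourable selection, and the working correlation decides how far the fit allows for this. Weighting by the inverse covariance is not weighting by the probability of response.

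Over five years of forms, score-related non-return is plausible: men with poor function, relapse or salvage treatment may stop replying.

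The direction matters because a slope that is not significantly negative counts as success. For SF-12 and EPIC, scored so that lower is worse (as the stated test presumes), losing men with low scores flattens a decline and favours the conclusion of maintained QoL. AUA runs the other way: in Appendix VI higher item scores mean worse symptoms. Losing badly affected men makes the AUA slope more negative, which also flatters the treatment but moves the estimate towards failing the stated test.

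**Working it through.** **1. The plan's own figure.** The documents give no number for the QoL analysis. The 8% allowance belongs to the bDFS sample size, which reproduces:

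N = [0.84 x sqrt(0.945 x 0.055) + 1.645 x sqrt(0.90 x 0.10)]^2 / (0.945 - 0.90)^2 = 231.7, so 232. Then 232/0.92 = 252.2, so 253.

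**2. Simulation in score points.** From the documents: 253 men; visits at 0, 1, 6, 12, 24, 36, 48 and 60 months; a straight-line model on all recorded scores without imputation. Assumed, because the documents give no values: true five-year change -6 points; between-man SD 20; residual SD 12; SD of the five-year slope 8 or 20; one-sided 5% test. Dropout starts at month 6 with logit = base - 1.0 x (last score - 70)/SD, which multiplies the odds by about 2.7 per SD lower last score. Base values of -4.7, -3.6 and -3.1 give about 9%, 22% and 31% dropout.

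Mean estimated five-year change (truth -6):

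| Method | Slope SD | 9% | 22% | 31% |
|---|---|---|---|---|
| GEE, independence | 8 | -4.5 | -2.4 | -0.2 |
| GEE, exchangeable | 8 | -5.9 | -6.0 | -5.6 |
| Likelihood, unstructured | 8 | -6.0 | -6.2 | -5.8 |
| GEE, independence | 20 | -4.0 | -0.9 | +1.3 |
| GEE, exchangeable | 20 | -5.5 | -4.7 | -4.3 |
| Likelihood, unstructured | 20 | -6.0 | -5.7 | -5.8 |

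The likelihood rows are baseline-to-60-month changes. The share of the decline lost is (6 - |estimate|)/6. For independence with slope SD 8 that is 1.5/6 = 25%, 3.6/6 = 60% and 5.8/6 = 97%. For exchangeable with slope SD 20 it is 0.5/6 = 8%, 1.3/6 = 22% and 1.7/6 = 28%.

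With slope SD 8, repeated runs of 150 to 300 simulated trials found the decline significant under independence in 98-100%, 49-67% and 6-9% of trials at the three dropout levels. Exchangeable GEE found it in 100% throughout.

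**3. A second setting, in SD units.** True slope -0.040 SD per year; dropout log-hazard 1.5 per SD of worse score (steeper than in step 2); 1000 trials per cell. Ranges cover two within-man covariances, random intercept alone and random intercept plus slope.

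| Dropout depends on | Method | 8% | 20% | 40% |
|---|---|---|---|---|
| Nothing | either GEE | about -0.040 | about -0.040 | about -0.040 |
| Last recorded score | independence | -0.028 to -0.023 | -0.012 to +0.001 | +0.017 to +0.042 |
| Last recorded score | exchangeable, correct | -0.040 | -0.039 | -0.038 |
| Last recorded score | exchangeable, misspecified | -0.034 | -0.027 | -0.014 |
| Current unseen score | exchangeable | -0.036 to -0.029 | -0.028 to -0.011 | -0.012 to +0.017 |

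When dropout is unrelated to QoL there is no bias. When it depends on recorded scores, the result turns on whether the working correlation is right.

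**4. Dropout on unseen scores, setting of step 2, slope SD 8.** Likelihood-type weighting with the true covariance gives -5.65, -5.2 and -4.9; exchangeable GEE gives -5.6, -5.1 and -4.8. Neither removes this bias.

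**The case against.** The largest figures come from independence GEE, which the plan does not describe. Its weighting by the inverse variance-covariance matrix, and its reference to correlation among a man's repeated values, point to a non-independence structure. With an exchangeable structure and slope SD 8, the estimates are close to the truth. This stands: it rules out the reading that GEE is valid only when dropout is unrelated to QoL, and it means the independence rows cannot be taken as a forecast for this trial.

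The dropout strength is also assumed. With odds x1.65 per SD and 17% dropout, even independence GEE gave -4.5 and found the decline in 99% of trials; with log-odds 0.3 per SD and 25% dropout it gave -4.5 and 98%. At about 9% dropout, close to the only loss rate stated, the step 2 setting still detected the decline in at least 98% of trials. This stands as a limit on size.

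A reader might infer that the plan says missing data need no handling, or that correlation does not matter. It says neither. It says that no imputation is required, which is equally true of a mixed model, and it claims validity in most cases, not all.

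What the objection does not remove is that the structure is unnamed and the validity statement carries no missing-data condition. Exchangeable GEE also loses part of the decline when slopes vary widely between men.

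**Conclusion.** The point holds as a gap in the secondary QoL analysis. The robustness claimed in section 11.4.2 is assured only if missing forms are unrelated to QoL. If return depends on earlier scores, the slope depends on an unspecified choice. Under the assumed settings the loss runs from almost nothing (exchangeable, slope SD 8) through 8-28% (exchangeable, slope SD 20) to 25-97% (independence, slope SD 8).

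A reader might infer that the plan would report a true decline as maintained QoL. The documents do not support that as an expectation. In the score-point simulations, losing most of the decline required independence weighting and strong score-related dropout of about 20% or more, and the documents give no rate of form return. With the steeper dropout of the second setting, a misspecified exchangeable structure loses 15% of the slope at 8% dropout (0.006/0.040) and 65% at 40% (0.026/0.040).

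Near 8-9% dropout the effect is modest: 8% or less for exchangeable GEE and 25% for independence in the score-point setting with slope SD 8 or, for exchangeable, up to 20. The 8% itself was set for bDFS, not for questionnaires. The bDFS and toxicity conclusions are unaffected. Reading a non-significant slope as maintenance, and testing AUA in the wrong direction, are separate weaknesses that a change of model would not cure.

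**What to change.** In section 11.4.2:

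- Estimate the same time trend with a likelihood-based repeated-measures model on all observed scores, with unstructured covariance or a random intercept and slope. It is valid when dropout depends on recorded scores, provided the model is correctly specified.
- Keep GEE as a sensitivity analysis, with a named working correlation and inverse-probability-of-response weights.
- Add a delta-adjusted or pattern-mixture analysis, because neither method above protects against dropout driven by unseen scores.
- Qualify the validity statement with the missing-data assumption it needs.
- Report form return by visit for each questionnaire.

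The cost is revised wording, slightly more modelling and more covariance parameters to estimate. The scores needed are already being collected.

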9.3. QUALITY OF LIFE ASSESSMENTS

- 9.3.1. SF-12: The SHORT FORM-12 Health Survey measures generic health status relevant across different age, disease, and treatment groups. It provides a comprehensive, psychometrically sound assessment of health status from the patient's point of view by scoring responses to standard questions. The SF-12 is self-administered, and can usually be completed in less than 3 minutes without assistance.
- 9.3.2. EXPANDED PROSTATE CANCER INDEX COMPOSITE (EPIC)-26: is a validated comprehensive instrument developed to assess patient function and bother after prostate cancer treatment. It was developed by an expert panel of urological oncologists, radiation oncologists (including those with brachytherapy expertise), survey researchers, and prostate cancer nurses, to address symptoms related to radical prostatectomy, external beam radiotherapy, prostate brachytherapy, and hormonal symptoms. See appendix VI.
- 9.3.3. AMERICAN UROLOGICAL ASSOCIATION (AUA) SYMPTOM INDEX: Also known as the International Prostate Symptom Score (IPSS), this widely used index assesses urinary symptom bother. See appendix VI.
- 9.3.4. SEXUAL HEALTH INVENTORY FOR MEN (SHIM): is a widely used, internationally validated and sensitive instrument for assessing erectile dysfunction¹.
- 9.3.5. UTILIZATION OF SEXUAL MEDICATIONS/DEVISES: provides context for interpreting the sexual domain score of the EPIC questionnaire.
- 9.4. CRITERIA FOR DISEASE CONTROL: intervals will be measured from enrollment date.
 - 9.4.1. BIOCHEMICIAL DISEASE-FREE SURVIVAL (bDFS): is measured as time to PSA failure. While earlier reports of prostate cancer patients treated with radiotherapy have used the ASTRO consensus definition (ACD) of PSA failure, recent studies^{2,3,4} have suggested the "nadir+2" definition is a more sensitive and specific definition of biochemical failure. Indeed, a recent expert panel met in Phoenix⁵ and developed a consensus recommendation using the later definition. So that comparisons can be made with earlier literature, both definitions shall be used:

П

- 9.4.1.1.Phoenix definition: failure occurs when the PSA is 2 ng/ml more than the lowest PSA measurement before the current one, with no backdating. Administration of salvage therapy (hormones, surgery, etc...) will be considered failure.

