Appendix VI: AUA, SF-12, EPIC, SHIM, USMD Questionnaires:

American Urological Association (AUA) symptom index: was developed to help men determine how bothersome their urinary symptoms are and to check the effectiveness of treatment.⁶ This questionnaire has also been adopted worldwide and is known as the International Prostate Symptom Score (IPSS). It is sometimes seen with a Quality of Life Scale at the end of the questionnaire.

Name:	Today's date:

(Circle one number on each line)	Almost never	Less than 1 time in 5	Less than half the time	About half the time	More than half the time	Almost always
Over the past month or so, how often have you had a sensation of not emptying your bladder completely after you finished urinating?	0	1	2	3	4	5
Over the past month or so, how often have you had to urinate again less than two hours after you finished urinating?	0	1	2	3	4	5
Over the past month or so, how often have you found you stopped and started again several times when you urinated?	0	1	2	3	4	5
Over the past month or so, how often have you found it difficult to postpone urination?	0	1	2	3	4	5
Over the past month or so, how often have you had a weak urinary stream?	0	1	2	3	4	5
Over the past month or so, how often have you had to push or strain to begin urination?	0	1	2	3	4	5
	None	1 time	2 times	3 times	4 times	5 or more times
Over the past month, how many times did you most typically get up to urinate from the time you went to bed at night until the time you got up in the morning?	0	1	2	3	4	5

 Quality of Life: If you were to spend the rest of your life with your urinary condition just the way it is now, how would you feel about that? Delighted, Pleased, Mostly satisfied, Mixed, Mostly dissatisfied, Unhappy, Terrible

SF-12 (Short Form)

 In general, would you say your health is excellent, very good, good, fair, or poor? Excellent ... Very Good ... Good ... Fair ... Poor ...

The following items are about activities you might do during a typical day. Does your health now limit you in these activities? If so, how much?

- 2) First, moderate activities such as moving a table, pushing a vacuum cleaner, bowling or playing golf. Does your health now limit you a lot, limit you a little, or not limit you at all. Limited a lot ... Limited a little ... Not limited at all ...
- 3. Climbing several flights of stairs. Does your health now limit you a lot, limit you a little, or not limit you at all? Limited a lot ... Limited a little ... Not limited at all ...

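### The only quality-of-life criterion, a slope not significantly below zero, runs backwards for the AUA score, and one straight line misreads the worsen-then-recover course the plan predicts for it

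*Combined protocol and SAP*

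**What the plan says.** Section 11.4.2 (Quality of Life Assessments) names the outcomes: "The SF-12 total score, AUA score, EPIC-26 total score and the EPIC-sexual domain sub score are used to quantify quality of life". The model is common to all four: "For each score, we will use GEE to fit a straight line to" the repeated values, with months as the explanatory variable. The conclusion is drawn from the slope: "We hypothesize that the slope of a fitted line will not be significantly less than zero; that is, QoL will be maintained" over the whole assessment period. The section gives no scoring direction, working correlation, significance level or margin for any of these scores.

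The same paragraph predicts two shapes. The urinary and bowel parts of the EPIC-26 and the AUA "will demonstrate a worsening of GU and GI function, but this will return to normal with time". The "sexual function subset of the EPIC-26 will show gradual worsening function relative to baseline over the five-year follow-up period".

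The AUA's direction is clear elsewhere. Section 9.3.3 says "this widely used index assesses urinary symptom bother". Appendix VI says it "was developed to help men determine how bothersome their urinary symptoms are" and prints items such as "Over the past month or so, how often have you had a weak urinary stream", scored from 0 (almost never) to 5 (almost always). No reverse scoring is stated.

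**The concern.** Equating a slope that is not negative with maintained quality of life presumes that higher is better. For the AUA the opposite holds, so the criterion accepts harm and rejects benefit. A single line also cannot describe a score that rises sharply and then recovers. It turns the early peak into a downward trend, so the plan's own predicted course fails the plan's own criterion.

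Section 1.12 says why this matters: it calls morbidity crucial to patient outcome and patient reports more sensitive than physician reports. This criterion is the only statement in the plan that turns those reports into a conclusion.

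**Working it through.** **Plan figures.** The plan gives no size, SD or power for quality of life, so there is no figure of that kind to reproduce. The one plan number used is N = 232. Formula 1 in section 11.3 gives [0.84√(0.945×0.055) + 1.645√(0.90×0.10)]² / 0.045² = 231.7, rounded up to 232.

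**Direction (no assumptions needed).** Higher AUA means more symptoms. A steady rise has a positive slope and counts as maintained. A steady fall has a negative slope and, if significant, counts as not maintained.

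**Slopes.** Visits in section 9.1.4: 0, last treatment day (assumed 0.23 months), 0.46, 1, 3, 6, 12, 18, 24, then every 6 months to 60. The section 9 table footnote gives 36, 48 and 60 after month 24. Assumed baseline: 8. Fitted 5-year change = 60·Σ(t−t̄)y / Σ(t−t̄)², or its generalised least-squares form when the working correlation is not independence. On the section 9.1.4 visits, t̄ = 22.31 and Σ(t−t̄)² = 6402.

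- Steady rise from 8 to 16: +8.0, passes.
- Immediate permanent step from 8 to 16: only the baseline differs, so 60×8×22.31/6402 = +1.7, passes.
- Predicted course, full recovery: a rise of A = 10 decaying as exp(−time since peak/6), with three onsets:

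| Weighting and visits | Peak on last treatment day | Linear ramp to month 1 | No rise before month 1 |
|---|---|---|---|
| Unweighted, section 9.1.4, to month 60 | -7.7 | -5.5 | -4.1 |
| Unweighted, section 9 table, to month 60 | -8.0 | -5.7 | -4.2 |
| AR(1) 0.7 by visit order, section 9.1.4 | -5.2 | -4.2 | -3.4 |
| AR(1) 0.7 by visit order, section 9 table | -4.5 | -3.7 | -3.0 |
| AR 0.9 per month, section 9.1.4 | -2.2 | -2.3 | -2.2 |
| Unweighted, section 9.1.4 plus years 6-10 | -3.3 | -2.5 | -1.9 |
| AR 0.9 per month, plus years 6-10 | -0.9 | -1.0 | -0.9 |

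A 5-point rise halves every entry. In the unweighted case to month 60, with SD 5 to 9 and exchangeable correlation 0.3 to 0.7, SE = 60·SD·√[(1−ρ)/(232×6402)] = 0.13 to 0.37. Even the 5-point, late-onset figure of -2.1 is then clearly significant.

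**Would reversing the sign be enough?** Let the course settle R points above baseline: R + (A−R)·exp(−time since peak/6). Section 9.1.4 visits to month 60, same three onsets:

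- A = 10, R = 3: unweighted -4.7, -2.4, -1.0; AR(1) 0.7 gives -2.5, -1.4, -0.6; AR 0.9 per month gives +0.1, +0.1, +0.2.
- A = 5, R = 2: unweighted -1.9, -0.7, 0.0; AR(1) 0.7 gives -0.8, -0.2, +0.2; AR 0.9 per month gives +0.5 throughout.

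So lasting worsening can still slope downward, depending on the working correlation.

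**Sexual domain and non-significance.** EPIC visits at 0, 1, 6, 12, 24, 36, 48 and 60 give Σ(t−t̄)² = 3586. Assume higher is better, one-sided 5%, 232 patients and no dropout.

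- Decline and a slope not significantly below zero coexist only if the fitted decline is below 1.645×SE: 1.645×0.54 = 0.9 points (SD 15, correlation 0.7) to 1.645×1.395 = 2.3 (SD 30, correlation 0.5).
- A steady 3-point loss passes with probability Φ(1.645 − 3/SE). At correlation 0.5, SD 15 (SE 0.698) gives 0.004 and SD 30 (SE 1.395) gives 0.31.

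**The case against.** The strongest reply is that this is a hypothesis and not a decision rule. Section 11.4.1 says in terms when the treatment will be considered effective or safe; section 11.4.2 only hypothesises. Section 2 sets the aim as measurement, comparison with other studies is planned, and an analyst holding the AUA form would see which way it runs. It stands that no success claim depends on this criterion. But the planned comparison has no rule, so the slope statement is the only route from these data to a conclusion. Choosing the direction after seeing single-arm data is what a plan should prevent.

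A second reply is that GEE is robust. Section 11.4.2 claims this for the distribution and the correlation structure; it does not extend to a wrong mean shape. When the line is wrong, the weights decide which slope is estimated, as the table shows.

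A third reply is that the sizes rest on assumed means, and that weighting and longer follow-up shrink them. That is correct. The sign of the full-recovery slope stayed negative in every case tried, but its size is not fixed.

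A reader might infer that a sign-reversed line must always mislead. The documents do not support that: no working correlation is named, and under AR 0.9 per month to month 60 the partial-recovery slopes were slightly positive. A reader might also infer that the two sexual-domain predictions flatly contradict each other. They can both hold, but only for a decline too small to be significant.

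**Conclusion.** Wrong as written, on a secondary objective.

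- The AUA reversal follows from the text alone.
- The predicted AUA course reads as not maintained. For an assumed 10-point rise with 6-month decay, the fitted 5-year change on the section 9.1.4 visits is about -7.7 to -4.1 unweighted to month 60, and about -3.3 to -1.9 with years 6 to 10. Across both visit schedules it is about -5.2 to -3.0 with AR(1) 0.7. With AR 0.9 per month it is about -2.3 to -2.2 to month 60.
- Reversing the sign alone may not be enough, depending on the working correlation.
- Reading non-significance as maintenance is unsound. A steady 3-point loss over 5 years passes in under 1% to about 31% of trials under the assumed SDs of 15 to 30, so it can be called neither harmless nor always serious.

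A reader might carry this over to the trial's main conclusions. The documents do not support that: the efficacy and safety tests in section 11.4.1 use none of these scores.

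**What to change.** In section 11.4.2:

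- State the direction of each score and reverse the test for the AUA, so that a positive slope means worsening.
- Keep GEE, but enter visit as a category, or model acute and late periods separately. Report mean change from baseline with its confidence interval at each visit.
- Base the quality-of-life statement on the late-period changes, allowing for the acute worsening the plan expects, and not on a non-significant slope. If the word maintained is kept, a tolerable change for each score would have to be set in advance; the documents give no value.
- Take the EPIC sexual domain out of the slope hypothesis and report its change from baseline.

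The cost is revised SAP wording and a few more model parameters, with no new data. Separately, AUA frequency after month 24 is every 6 months in section 9.1.4 and every 12 months in the section 9 table footnote; the two should be reconciled.

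### Section 11.4.2 reads a non-significant quality-of-life slope as proof of maintenance, and does not exempt the sexual score it predicts will worsen

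*Combined protocol and SAP*

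**What the plan says.** Section 11.4.2, item 2, names the outcomes: "The SF-12 total score, AUA score, EPIC-26 total score and the EPIC-sexual domain sub score are used to quantify quality of life". The model applies to all of them: "For each score, we will use GEE to fit a straight line to patients' longitudinal course of repeated values". The hypothesis that closes the item is "We hypothesize that the slope of a fitted line will not be significantly less than zero; that is, QoL will be maintained" over the assessment period, and no score is exempted. Earlier in the same paragraph the plan says: "We further hypothesize that the sexual function subset of the EPIC-26 will show gradual worsening function relative to baseline over the five-year follow-up period".

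On missing forms the text says only: "With this method, no imputations are required and all data recorded is use in the analysis". It states no missing-data assumption and no sensitivity analysis. For quality of life there is no decline margin, minimal important change, confidence-limit criterion, significance level or power.

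The primary objectives are handled differently. Section 11.4.1 requires a one-sided 95% confidence limit to clear a fixed bound: the lower limit for bDFS must not be below 90%, and the upper limit for toxicity must not be more than 5 points above 9%. Section 11.3 accordingly asks for 95% confidence that the Grade 3 or higher toxicity rate "is not more than 5% higher than the approximately 9% 5-year rate extrapolated from Table 2".

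**The concern.** Failure to reject a zero slope may mean that there was little decline, or that the data could not show one. The plan's sentence does not separate the two. It makes non-significance the meaning of maintenance and offers no other criterion. The less information the questionnaires carry, the wider the standard error and the more likely the favourable reading.

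The sexual sub-score adds a contradiction. The analysis set and the closing hypothesis cover it, so the plan expects its slope both to show worsening and not to be significantly negative.

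What is at stake is how patient-reported results are described. Section 1.12 calls treatment morbidity crucial to patient outcome and regards patient reports as more sensitive than physician reports. Section 1.14 puts forward better potency preservation than HDR brachytherapy, and section 14.5 lists reduced sexual toxicity as a possible benefit. A statement that quality of life was maintained would be read beside those claims.

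**Working it through.** **Plan's own figures.** The only sample size is for bDFS, with "power equal to 80% at the one-sided 5% significance level". Formula 1 with null rate 0.90, alternative 0.945, z = 1.645 and 0.84:

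[0.84 × √(0.945 × 0.055) + 1.645 × √(0.90 × 0.10)]² / 0.045² = 231.7, so 232. Then 232/0.92 = 252.2, so 253. Both reproduce. The section 11.4.1 upper limit for 9% observed toxicity in 232 patients is 12.6%, as stated. There is no quality-of-life figure to reproduce.

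**Inputs for the slope rule.**
- From section 9.1.4 and the assessment table: EPIC-26 and SF-12 at 0, 1, 6, 12, 24, 36, 48 and 60 months. In five-year units the sum of squares of time is Sxx = 0.996.
- Assumed, not in the documents: score SD = 1; within-patient correlation 0.5; between-patient slope SD s of 0.5 to 1.0 SD per five years; a one-sided 5% test; n = patients with complete forms; lower scores are worse.

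**Formulas.** SE = √{[(1 − 0.5)/0.996 + s²]/n}. For a true decline d, P(read as maintained) = 1 − Φ(d/SE − 1.645).

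With s = 0.5, n = 232 and d = 0.2: SE = √(0.752/232) = 0.057; 0.2/0.057 − 1.645 ≈ 1.87; P = 3%. With s = 1.0: SE = √(1.502/232) = 0.080; P = 20%.

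P(read as maintained), for s = 0.5 to 1.0:

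| True five-year decline | n = 232 | n = 100 | n = 25 |
|---|---|---|---|
| 0.2 SD | 3% to 20% | 25% to 51% | 69% to 80% |
| 0.3 SD | under 0.1% to 2% | 4% to 21% | 47% to 66% |

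For any true decline the probability rises as n falls. That direction does not depend on the assumed values.

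**What a margin rule does instead.** Take an illustrative margin of 0.3 SD and require the lower one-sided 95% limit to lie above −0.3. A true decline equal to the margin passes 5% of the time at every n. With no true decline, the rule passes about 98% to 100% of the time at n = 232, 79% to 97% at n = 100 and 34% to 53% at n = 25. Losing data now makes the claim harder to reach.

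**The margin has to be chosen with care.** Consider a margin of half the baseline SD and a simple change score whose SD equals the baseline SD. At n = 232, SE = 1/√232 = 0.066. The present rule tolerates an observed decline of up to 1.645 × 0.066 = 0.11 SD; the half-SD rule tolerates 0.50 − 0.11 = 0.39 SD. A true decline of 0.3 SD passes about 0.2% of the time under the present rule and about 92% under the half-SD rule. The half-SD rule is the looser one whenever 3.29/√n < 0.5, that is, for n of 44 or more.

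**The case against.** The plan says it hypothesizes, not that it will conclude. Section 2 describes the quality-of-life objective as one of measurement. Formal success criteria exist only for the primary endpoints, and those do use confidence limits. Quality-of-life results will also be compared with other prospective studies, and no trial decision turns on this sentence. All of that stands and limits the severity. It does not supply another criterion: the sentence equates non-significance with maintenance, and the section offers nothing else by which to judge the hypothesis.

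It is also fair that the plan allows 8% loss and aims for 232 evaluable patients. The smaller sizes in the table are assumptions; the documents give no expected questionnaire return rate.

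The specific prediction for sexual function could be read as an exception to the general closing sentence. That is a plausible intention, but the text does not say so.

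Three stronger readings are tempting and are not supported:
- A reader might infer that any decline inside the confidence limit would be called maintained. When the estimate sits exactly on the significance boundary, the limit is at 2 × 1.645 = 3.29 standard errors. A decline that large could not be excluded by such a result, but if it were the truth, a non-significant slope would occur only about 5% of the time.
- A reader might infer that every sexual-function result would count as predicted. An improving score would contradict the worsening prediction, and a significant fall would contradict maintenance.
- A reader might assume that any margin rule is stricter than the present one. The half-SD calculation shows otherwise at the planned size.

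**Conclusion.** The inference is wrong as written, for a secondary objective. Non-significance of a negative slope is not evidence of maintenance, and the rule rewards imprecision. The two statements on the sexual sub-score conflict and must be reconciled.

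The size depends on completeness. With near-complete forms from 232 patients the practical harm is modest: a 0.3 SD decline is nearly always detected and a 0.2 SD decline is missed 3% to 20% of the time. With complete forms from only 100 patients, the latter becomes 25% to 51%. These percentages rest on the assumed SD, correlation, slope variance and one-sided 5% level. They reflect lost precision only; if forms are missing for reasons related to quality of life, the slope could also be biased in either direction. The logical error and the contradiction rest on the text alone.

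**What to change.** In section 11.4.2, item 2:

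1. For each score, report the estimated change or slope with a 95% confidence interval, and state that a non-significant slope will not be taken as maintenance.
2. Use the word maintained only if the confidence limit on the worsening side excludes a decline margin that the sponsor justifies for that instrument and fixes before analysis. This follows the confidence-limit logic of section 11.4.1. Otherwise report the result as inconclusive. For the AUA score, whose items run from 0 (almost never) to 5 (almost always), the worsening side is the upper limit.
3. Remove the EPIC sexual sub-score from the maintenance hypothesis and report its change with an interval.

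The cost is wording: the GEE fit already gives the intervals, and no new data are needed. The downside is that a margin must be justified for each instrument, and some results will have to be reported as inconclusive.
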